## 16. Adverse Event Analysis

All adverse events and serious adverse events will be analyzed to determine likelihood of association with treatment. Likely and known Treatment Emergent Events will be tabulated and summarized by presenting the incidence number (number and percentage of subjects) in each treatment group. No inferential analyses will be performed on safety parameters.

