### Exclusion Criteria

1. Refusal to provide informed consent
2. Pregnant or breastfeeding women
3. Diarrhea prior to infection
4. Negative test for COVID-19 by RT-PCR or rapid antigen test at screening
5. Any comorbidities which, in the opinion of the investigator, constitute health risk for the subject
6. Any contraindications for treatment with hydroxychloroquine
  - a. Hypoglycemic
  - b. Known G6PD deficiency
  - c. Porphyria
  - d. Anemia
  - e. Neutropenia
  - f. Alcoholism
  - g. Myasthenia gravis
  - h. Skeletal muscle disorders
  - i. Maculopathy
  - j. Changes in visual field
  - k. Liver disease
  - l. Psoriasis
  - m. History of QT interval >500msec
  - n. History of torsades de pointes
7. Anemia from pyruvate kinase and G6PD deficiencies
8. Abnormal EKG with QT prolongation acquired or from birth
9. Allergies to 4-Aminoquinolines
10. History of jaundice or high fevers prior to developing COVID-19
11. Treatment with any of the medications listed in Appendix II
12. Treatment with any other drug not listed that affects the QT interval
13. Treatment with any anti-epileptics

ProgenaBiome, LLC Protocol PRG-044	21 July2020
Number of Subjects	
Subjects will be enrolled to ensure that at least 600 complete the study. It is anticipated that screening of 1200 Subjects will be required to achieve this.	
Specimen Requirements:	
NP swabs (synthetic swab on plastic shaft) placed into 2-3mL of viral transport media. 1 mL of blood in an EDTA and 2 mL of serum in two serum separator tubes spun down	
Study Duration	
Screening of 1200 Subjects and enrollment of 600 Subjects is expected to take 3 months	

Primary Study Objective	Study Endpoints
The rate of recovery from COVID-19 in Subjects using Quintuple Therapy	Number of days from COVID-19 diagnosis to recovery via RT-PCR
Reduction or Progression of Symptomatic Days	Reduction and/or progression of symptomatic days, reduction of symptom severity
Secondary Objectives	Study Endpoints
Assess the safety and Tolerability of Quintuple Therapy	Assess the symptom response to study therapy as measured by the survey in the EDC
	EKG response, oxygen saturation, and vital signs at baseline, 2 weeks, 1 month, and two months
	Assess Adverse Events and Serious Adverse Events due to Quintuple Therapy

- a. Adverse event monitoring will be conducted for 12 weeks
- b. Serious adverse event monitoring will be conducted for 12 weeks

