### 11.1 Unexpected Adverse Events

An unexpected AE, the nature, severity, specificity, or outcome of which is not consistent with the summary of product characteristics described in the Product Insert

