#### **11.5 Relationship to Study**

The investigator must determine the relationship between the administration of study drug and the occurrence of an AE/SAE as Not Suspected or Suspected as defined below. Factors for the assessment of causal relationship include, but are not limited to, the temporal relationship between the AE and the administration of study drug, known side effects of study drug, concomitant therapy, course of the underlying disease and pertinent study procedures.

- Not Suspected: Means a causal relationship of the AE to study drug administration is unlikely or remote, or other medications, therapeutic interventions, or underlying conditions provide a sufficient explanation for the observed event
- Suspected: Means there is a reasonable possibility that the administration of study drug caused the AE. "Reasonable possibility" means there is evidence to suggest a causal relationship between the study drug and the AE.

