## 15. Statistical analysis

The treated patients in this study will be compared to the placebo group. Measurements will include PCR test results, presence or absence of symptoms, and symptom severity. PCR results will be compared between the groups as positive or negative

In this study, the meaningful threshold will be calculated as mean change in clinical symptoms as recorded in the diary, from Day 1 through week 12. Each category in the diary will be assigned a number, 0 for None, 1 for Mild, 2 for Moderate and 3 for severe. Each category will be analyzed independently and they will be analyzed as a group. Ultimately, efficacy will be determined based upon reduction and/or progression of symptomatic days, reduction of symptom severity, as well as analysis of the subject's RT-PCR testing per protocol. These data will be compared to an existing database of de-identified Subject data.

The change of these measurements from the end to the baseline (post-pre) will be used as the primary outcome, for example,  $\mu_e = \mu_{e1} - \mu_{e0}$ , where  $\mu_{e1}$  and  $\mu_{e0}$  are the outcome of Subjects from the treatment group at the end and at baseline, respectively.

Categorical variables will be summarized by presenting the number (n) and percent (%) of subjects in each category. All Statistical tests for the analysis will be performed using the  $p < 0.05$  level of significance. All confidence intervals will be one-sided

Sample size was calculated as follows:

$$n = \frac{\log \beta}{\log \rho}$$

Where  $\beta = \text{the probability of a Type II error}$

$\rho = \text{the proportion of the population NOT affected}$

The proportion of the population affected by COVID-19 is 0.005 percent, thus 0.995 percent aren't affected

The probability of a type II error is 0.05

Thus:

$$n = \frac{\log 0.050}{\log 0.995}$$

$$n = 597.647$$

A sample size of 600 will be used

Additional details can be found in the Statistical Analysis Plan that will be developed prior to database lock.

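### Section 16 promises by-arm adverse event counts only through an undefined attribution filter, and the EKG, oxygen and vital-sign endpoint does not match the visit schedule

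*Combined protocol and SAP*

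**What the plan says.** **Adverse events.** Section 16 has two relevant sentences. The first says that all adverse and serious adverse events "will be analyzed to determine likelihood of association with treatment". The second makes the only tabulation promise, a number and percentage in each treatment group: "Likely and known Treatment Emergent Events will be tabulated and summarized". It is followed by a statement that safety will not be tested inferentially.

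Section 11.5 requires the investigator to classify each event "as Not Suspected or Suspected as defined below". The definition of Suspected reads "Means there is a reasonable possibility that the administration of study drug caused the AE". Section 11 defines an adverse event without requiring a causal link, and Section 11.6 has events recorded from consent onwards. The matching secondary endpoint, in the Synopsis objectives table and in Section 2, is "Assess Adverse Events and Serious Adverse Events due to Quintuple Therapy".

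**EKG, oxygen and vital signs.** The endpoint in the same two tables is "EKG response, oxygen saturation, and vital signs at baseline, 2 weeks, 1 month, and two months". The Schedule of Events (Section 6) marks home readings, which footnote e defines as EKG, oxygen saturation and temperature, on Days 1 to 10. It marks clinic vitals and EKG at Months 1, 2 and 3.

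**Deferral.** Section 15 ends: "Additional details can be found in the Statistical Analysis Plan that will be developed prior to database lock". The document supplied contains no such plan.

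**The concern.** Safety and tolerability is the trial's secondary objective. The design has a concurrent randomised placebo arm, so a comparison of all events by arm needs no judgement about what caused each one. Section 16 nevertheless puts such a judgement between the recorded events and the table, and expresses it in words that the protocol does not define and its causality scale does not use. Two analysts working from the same database could build different tables and both claim to follow the plan.

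The EKG, oxygen and vital-sign endpoint has a different fault: its time points and the schedule do not agree. It names a reading that the schedule does not list, and it omits most of those taken while hydroxychloroquine or its placebo is being given. QT prolongation is a listed hydroxychloroquine risk in Section 13.1, and QT values appear among the subject stopping criteria in Appendix 4. The on-treatment readings are therefore relevant to safety, but the protocol names no by-arm summary of them. Under Section 11, an abnormal EKG finding becomes an adverse event only if it comes with symptoms, leads to discontinuation or is judged clinically relevant. The adverse event table cannot stand in for a summary of the readings.

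**Working it through.** The plan gives no figure on this point to reproduce. The check sets the sections side by side and counts time points.

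**Step 1: what the tabulation sentence admits.** At least three readings are open:

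- (a) *Likely* and *known* both grade association with treatment. The preceding sentence in Section 16, which is about association, supports this.
- (b) *Likely* grades association, and *known* means an effect listed for the product. Section 11.1 has a related idea: it calls an event unexpected when it "is not consistent with the summary of product characteristics described in the Product Insert".
- (c) *Known* means established as treatment-emergent, whatever the cause.

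Consider two events that are both judged Not Suspected. The first is a pneumonia, which Section 13.1 lists as an azithromycin risk and Section 1 describes as part of severe COVID-19. Section 11.5 allows Not Suspected when an underlying condition explains the event. The second is an event not listed for any study product.

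| Reading | Pneumonia, Not Suspected | Unlisted event, Not Suspected |
|---|---|---|
| (a) | not tabulated | not tabulated |
| (b) | tabulated | not tabulated |
| (c) | tabulated | tabulated |

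The same data give three different tables. The Section 11.5 scale does not settle which is meant, because a reasonable possibility of causation is not the same standard as *likely*.

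**Step 2: is there an all-causality table elsewhere?** Section 16 is the only adverse event analysis text. Section 15 has a general sentence on summarising categorical variables, but it names neither adverse events nor arms. The measurements that Section 15 lists for comparison between groups are PCR results, presence of symptoms and symptom severity.

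**Step 3: endpoint times against scheduled readings** (Synopsis, Sections 2, 3 and 6).

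| Time | Named in endpoint | Home EKG, oxygen, temperature | Clinic vitals and EKG |
|---|---|---|---|
| Day 1 (baseline) | yes | yes | no |
| Days 2-10 | no | yes | no |
| Day 14 (2 weeks) | yes | no | no |
| Month 1 | yes | no | yes |
| Month 2 | yes | no | yes |
| Month 3 | no | no | yes |

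For Day 14, Section 3 lists a call, a swab, the diary and the supplements.

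- Named time points: 4. With a scheduled reading: 3. Without: 4 - 3 = 1.
- Home-reading days: 10. Outside the endpoint if Day 1 is baseline: 10 - 1 = 9. These are 4 days (Days 2-5) with azithromycin or placebo also taken, and 5 days (Days 6-10) with hydroxychloroquine or placebo but no azithromycin.
- Section 3 also says that screening values will be compared with later ones. If screening is the baseline, 10 of 10 home-reading days fall outside.

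Taking Day 1 as baseline, that is the only endpoint reading within the hydroxychloroquine-or-placebo course. The next endpoint reading that is actually scheduled is Month 1, where Section 3 marks the EKG optional.

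**Step 4: could a 2-week reading exist anyway?** The Synopsis has the EKG used daily for 10 days. Footnote b of the schedule describes the device as worn without interruption and gives no end day. The Synopsis gives no end day for pulse-oximeter reporting either. The documents leave this unresolved.

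**The case against.** The strongest reply is that nothing is lost yet. All adverse events go onto the eCRF whatever their cause, and the promised SAP can add all-causality tables and a Day 1-10 summary before database lock. That stands for the tables, so this is a gap in what is committed and not evidence that data will go unreported. It does not cure the 2-week mismatch, because an analysis plan cannot schedule a reading.

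A second reply is that *known* is too vague to prove exclusion. This also stands. A reader might infer that even the broadest interpretation leaves unexpected, unattributed events out of every table. The documents do not support that, since reading (c) would count them. What is supportable is that the wording is ambiguous and, on its natural causal reading, may exclude events.

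Third, a reader might infer that the 2-week reading will never be collected. Footnote b and the open-ended oximetry leave that unclear. The documents show only that no such reading is listed.

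Fourth, the endpoint phrase about events due to the therapy need not be a filter, because in a randomised trial comparing arms is one way to judge what is due to treatment. That is fair. The phrase should be aligned with the table, but it is not independent proof of a restriction.

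Finally, Section 3 says that screening values will be compared with values obtained later. It names no arms, time points or summary, so it does not fill the gap.

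**Conclusion.** The point holds in two parts, and both should be settled before the SAP is finalised.

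1. The only by-arm adverse event table that the protocol promises depends on undefined terms that do not match its own causality scale. On the natural reading it may omit events not attributed to treatment, and no section commits to an all-causality table by arm.
2. One of the 4 named time points for the EKG, oxygen and vital-sign endpoint has no scheduled reading. The endpoint also omits readings that are scheduled: Days 2-10 (9 of 10 home-reading days if Day 1 is baseline, 10 of 10 if screening is) and Month 3.

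The number of events that the filter would remove cannot be computed, because the documents give neither an adverse event rate nor an expected share of attributed events. A reader might go on to infer that the safety comparison is biased in favour of the active arm. The documents do not support that: attribution is made in a double-blind trial, and no direction of bias or loss of power is claimed.

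The inconsistent optional labels are a lesser, editorial matter. Follow-up EKG is optional in Section 3 but unlabelled in the schedule, and follow-up vitals are optional in schedule footnote f but not in Section 3.

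**What to change.** **Section 16.** Delete the *likely* and *known* qualifiers. Tabulate all treatment-emergent adverse events and serious adverse events by randomised arm regardless of causality (n, %), with Suspected events, as defined in Section 11.5, as a subset. Define treatment-emergent, for example as onset or worsening after the first dose. The definition matters because events are recorded from consent, before dosing, and the term is undefined at present. Align the adverse event endpoint wording in the Synopsis and Section 2 with this table.

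**Synopsis and Section 2.** Add a descriptive by-arm summary of the Day 1-10 EKG, oxygen saturation and temperature readings. Include QT change from a stated baseline (screening or Day 1) where the recordings provide it.

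**Reconcile** across the Synopsis, Section 2, Section 3 and the Section 6 schedule with its footnotes b, e and f: the 2-week and Month 3 time points, the duration of home EKG and oximetry, and the optional status of follow-up EKG and vitals. Which way to resolve each is for the sponsor. Carry the result into the SAP.

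**Cost.** Extra descriptive tables and some EKG data processing. The adverse events are already on the eCRF, and oxygen and temperature need only a summary table. EKG is the larger item: the Synopsis promises a cardiologist reading before dosing, but the documents do not show that a QT value is extracted from each daily recording. The additions are descriptive, so the statement that safety will not be tested inferentially can stand.

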## 2. Trial Objectives

Primary Study Objective	Study Endpoints
The rate of recovery of mild or moderate COVID-19 in Subjects using Quintuple Therapy	Number of Days Recovery from COVID-19 diagnosis to Recover via RT-PCR
Secondary Objectives	Study Endpoints
Assess the safety of Quintuple Therapy	Assess the symptom response to study therapy as measured by the survey in the EDC
	EKG response, oxygen saturation, and vital signs at baseline, 2 weeks, 1 month, and two months
Assess Tolerability of Quintuple Therapy	Assess Adverse Events and Serious Adverse Events due to Quintuple Therapy

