## 3. Study Procedures:

- Diagnosis, Medical Review, and Prescription of Therapy (Screening, Day -3 to Day -1):
  - Subject will provide electronic informed consent via the EDC portal.
  - Medical Information
    - a. Study staff will review prior and concomitant medications, including over-the-counter medications and supplements.
    - b. Investigator will review the Subject's records during the screening process, looking at inclusion/exclusion criteria, gathering data on vital signs, EKG recordings, and oxygen saturation. These values will be used to compare to values obtained throughout the study. If any contraindication to participation is found, the study drugs will not be provided and the subject will be deemed a screen failure.
  - Diagnosis of COVID-19 will be confirmed
    - a. May be based on PCR testing results, rapid antigen testing results, or clinical presentation at screening as assessed by the Principal Investigator including symptoms such as:
      - Fever
      - Cough
      - Anosmia
  - Subject will be provided a daily diary for recording symptoms.
  - Subject will be randomized into Arm 1 or Arm 2
  - Prescription of treatment drugs
    - a. Arm 1: Medications will be prescribed for Quintuple Therapy
      - Hydroxychloroquine 200MG BID for 10 days, Azithromycin 500mg on day 1, 250mg day 2-5, Vitamin C 3000mg for 10 days, then 1500mg for 20 days, Vitamin D 3000IU for 10 days, then 1500IU for 20 days, and zinc 50mg for 10 days, then 25mg for 20 days.
    - b. Arm 2: Placebos and supplements will be provided (to ensure nutritional parity)
      - Placebo for Hydroxychloroquine BID for 10 days, Placebo for Azithromycin to be taken 2 the on Day 1, then 1 on Days 2-5, Vitamin C 3000mg for 10 days, then 1500mg for 20 days, Vitamin D 3000IU for 10 days, then 1500IU for 20 days, and zinc 50mg for 10 days, then 25mg for 20 days.
    - c. Drugs shall be taken first thing in the morning as soon as the patient has eaten. Vitamins will be taken with lunch and dinner, and then the evening dose of drugs will be right before bed.
  - Monitoring equipment provided
    - a. Home EKG recording device

- b. Pulse Oximeter
    - c. Thermometer
    - d. Urine Pregnancy test if applicable
  - Subject will be isolated as an outpatient
    - a. All CDC recommendations regarding self-quarantine must be followed
- Treatment Period
  - Day 1 following positive test (isolation)

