- Temperature

- d. Subject will take prescribed regimen

Drug	AM Dose	PM Dose
Hydroxychloroquine (or Placebo)	200mg	200mg
Vitamin C	1500mg	1500mg
Vitamin D	1500IU	1500IU
Zinc	25mg	25mg

- o Day 11-Day 13

- a. Subject will complete AM/PM diaries

- b. Subject will take prescribed regimen

Drug	AM Dose	PM Dose
Vitamin C	750mg	750mg
Vitamin D	750IU	750IU
Zinc	12.5mg	12.5mg

- o Day 14

- a. Subject will be called

- Remind them to collect nasal or oropharyngeal swab
- Ask about AE/SAE
- Symptom resolution or progression
- Answer any questions the Subject may have

- b. Subject will collect nasal or oropharyngeal swab

- c. Subject will complete AM/PM diaries

- d. Subject will take prescribed regimen

Drug	AM Dose	PM Dose
Vitamin C	750mg	750mg

Vitamin D	750IU	750IU
Zinc	12.5mg	12.5mg

- Day 15-30
  - a. Subject will complete AM/PM diaries
  - b. Subject will take prescribed regimen

Drug	AM Dose	PM Dose
Vitamin C	750mg	750mg
Vitamin D	750IU	750IU
Zinc	12.5mg	12.5mg

- Follow-Up Period (These visits can be conducted via videoconference or in person)
  - Month 1 (outpatient only AFTER negative test)
    - a. Vital signs (BP, HR, RR, oxygen saturation, temperature)
    - b. Assessment for AE and SAE
    - c. EKG (Optional)
    - d. Physical exam (Optional)
    - e. Blood draw for CBC/Complete metabolic panel/C-Reactive Protein/Blood hydroxychloroquine levels/SARS-CoV Antibody test (All optional)
      - Blood HQ levels will remain blinded from all but unblinded coordinator
    - f. Update list of prior and concomitant medications
    - g. Study team will collect nasal or oropharyngeal swab (If patient elects to refrain from this in-person visit they will collect this at home)
  - Month 2 (outpatient)
    - a. Vital signs (BP, HR, RR, oxygen saturation, temperature)
    - b. Assessment for AE and SAE
    - c. EKG (Optional)
    - d. Physical exam (Optional)
    - e. Blood draw for CBC/Complete metabolic panel/C-Reactive Protein (Optional)
    - f. Update list of prior and concomitant medications
  - Month 3 (outpatient)
    - a. Vital signs (BP, HR, RR, oxygen saturation, temperature)
    - b. Assessment for AE and SAE
    - c. EKG (Optional)
    - d. Physical exam (Optional)
    - e. Blood draw for CBC/Complete metabolic panel/C-Reactive Protein (Optional)
    - f. Update list of prior and concomitant medications

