- e. To include EKG, oxygen saturation, and temperature
- f. Vitals in-clinic to include height (only at first visit), weight, blood pressure (following 5 minutes sitting) pulse, respiratory rate, temperature, and oxygen saturation (Optional)
- g. To include CBC, Complete Metabolic Panel, and CRP (details in section 9 Sample Collection) (Optional)

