## 11. Adverse Events and Serious Adverse Events

An AE is any untoward medical occurrence in a clinical investigation participant administered a study drug, which does not necessarily have a causal relationship with this treatment. An AE can therefore be any unfavorable and unintended sign (including an abnormal laboratory finding), symptom, or disease temporally associated with the use of the study drug whether or not it is considered related to the study drug.

If the Subject has any abnormal laboratory and other abnormal investigational findings (e.g., physical examination, ECG) should not be reported as AEs unless they are associated with clinical signs and symptoms, lead to treatment discontinuation, or are otherwise considered clinically relevant by the investigator.

In cases of surgical or diagnostic procedures, the condition/illness leading to such a procedure is considered as the AE rather than the procedure itself. In the case of a fatality, the cause of death is considered as the AE, and the death is considered as its outcome.

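### The only by-arm adverse-event table the plan commits to covers an undefined causality class; all treatment-emergent events should be tabulated by arm, with the Suspected subset beside them

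*Combined protocol and SAP*

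**What the plan says.** Section 16 (Adverse Event Analysis) does three things. It says all adverse events, serious or not, will be assessed for how likely they are to be associated with treatment. It then commits to a table: "Likely and known Treatment Emergent Events will be tabulated and summarized by presenting the incidence number (number and percentage of subjects", by treatment group. Finally, it rules out inferential analysis of safety.

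Section 11.5 defines the causality judgement that is recorded. The investigator judges the link between study drug and "the occurrence of an AE/SAE as Not Suspected or Suspected as defined below". Suspected means a reasonable possibility of causation. Not Suspected means that a link is improbable or that something else explains the event well enough.

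Section 2 lists the corresponding secondary endpoint as "Assess Adverse Events and Serious Adverse Events due to Quintuple Therapy"; the synopsis has the same wording.

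Section 15 names PCR and symptom measurements, gives a general count-and-percentage rule for categorical variables, and defers further detail to a SAP to be written before database lock. That SAP is not in the supplied text.

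**The concern.** The two words that decide what enters the table are defined nowhere, and neither is a level of the recorded scale. Two programmers working from the same database could produce different tables.

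Under any reading, the table is also restricted by causality. A placebo arm makes individual attribution unnecessary for the main safety display: if the drugs cause harm, the total event rate is higher in Arm 1, whoever judged each case. A table limited to attributed events shows instead what the assessors already believed the drugs could do. An excess of events put down to COVID-19 or another cause would not appear. Because safety is only described and not tested, what is tabulated is all that a reader of the results will see. Safety and tolerability are the secondary objective, and Section 13.1 lists serious cardiac, marrow and liver effects among the risks of the randomised drugs.

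**Working it through.** The plan contains no safety figure to reproduce, so the check is mainly a comparison of texts.

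**Step 1: can the Section 16 class be mapped to Section 11.5?** At least three readings fit:

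- The class is simply another name for Suspected.
- It is narrower than Suspected, because a reasonable possibility is a lower bar than likelihood in ordinary usage.
- The second term means already described for the product. Section 11.1 uses the product insert in this way to define unexpected events. New kinds of event would then be left out.

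Nothing in the documents chooses among these. All three exclude events judged Not Suspected.

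**Step 2: is there another by-arm table that would show the excluded events?** Sections 11.6 and 11.7 require all AEs to be recorded on the case report form. Appendix 3 says side effects are recorded as AEs or SAEs and describes individual care. The count-and-percentage rule in Section 15 names no safety variable. None of these commits to an all-causality table by arm.

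**Step 3: what the filter does to a visible excess (illustration).** Every input is assumed. True rates of subjects with an event are 10% in Arm 1 and 5% in Arm 2, a difference of 5 points and a ratio of 2. A share *s* of these subjects enters the class, the same in both arms. Rate shown = true rate × *s*.

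| *s* | Arm 1 shown | Arm 2 shown | Difference | Ratio |
|---|---|---|---|---|
| 25% | 0.25 × 10% = 2.5% | 0.25 × 5% = 1.25% | 1.25 points | 2 |
| 50% | 5.0% | 2.5% | 2.5 points | 2 |
| 75% | 7.5% | 3.75% | 3.75 points | 2 |

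**Step 4: the same rates, with attribution depending on the kind of event.** Split Arm 1 into 5% background events, as in Arm 2, and 5% drug-caused events. Let *b* be the share of background events and *e* the share of drug-caused events that enter the class. Arm 1 shown = 5% × *b* + 5% × *e*; Arm 2 shown = 5% × *b*.

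- Good attribution, *b* = 25% and *e* = 75%: Arm 1 = 1.25% + 3.75% = 5.0%, Arm 2 = 1.25%. The difference is 3.75 points and the ratio 4.
- Poor attribution, *b* = 75% and *e* = 25%: Arm 1 = 3.75% + 1.25% = 5.0%, Arm 2 = 3.75%. The difference is 1.25 points and the ratio 5.0/3.75 = 1.33.

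Blinding is respected in both cases. The filter helps the ratio when assessors recognise the drug's effects and hurts it when they do not. The all-causality table shows 10% and 5% in either case.

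**The case against.** The best defence is that Section 16 opens with its own step assessing how likely each event is to be associated with treatment, and that AE reports must record relationship and other possible causes. A reader might infer from the mismatch with Section 11.5 that the class cannot be built at all. The documents do not support that: a route exists, though no scale or rule for it is stated. What stands against the plan is the missing definition and the restriction by causality.

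Section 16 also does not forbid other tables, and the later SAP may add them. That is fair, but the sentence that is there commits only to the restricted table, and the deferral in Section 15 does not lift the restriction. It can further be said that filtering removes COVID-19 noise. It can, but only if attribution is good, as Step 4 shows.

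Three stronger readings are tempting:

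- **That the endpoint wording is itself a case-level filter.** Assessing harm due to a therapy is also what a comparison with placebo does, so that wording can stay.
- **That the plan sets out to hide late laboratory abnormalities.** Section 11 does keep abnormal findings out of the AE record "unless they are associated with clinical signs and symptoms, lead to treatment discontinuation, or are otherwise considered clinically relevant by the investigator", and no laboratory table is stated. But Appendix 3 points towards recording side effects generally, including blood and liver abnormalities. The blood tests are optional and not an endpoint: the Month 2 and 3 entries read "Blood draw for CBC/Complete metabolic panel/C-Reactive Protein (Optional". The absence of a stated laboratory table is missing detail that a SAP can supply, and is not itself an error.
- **That the filter favours the active arm.** Causality is judged in a double-blind trial, and nothing in the documents indicates a direction.

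**Conclusion.** The concern holds as a minor fault in the safety analysis. The by-arm table to which Section 16 commits is limited to an undefined class that does not match the recorded causality scale. It therefore rests on case-level attribution and, as written, leaves out events judged unrelated.

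The size cannot be estimated from the documents. On the assumed rates above, a 5-point difference would show as 1.25 to 3.75 points. The ratio would be unchanged if attribution is equal across events, and would run from 1.33 to 4 if it is not. These figures illustrate the mechanism and are not predictions. No efficacy conclusion is affected.

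**What to change.** Replace the tabulation sentence in Section 16 with: *All treatment-emergent AEs and SAEs will be tabulated by arm as number and percentage of subjects who took at least one dose, regardless of attributed causality; the Suspected subset (Section 11.5) will also be shown.*

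This uses the recorded scale, needs no new data and fixes the denominator. The denominator should be stated because subjects are randomised before the drugs are shipped and before the pre-dose EKG is read, so some may never start treatment. The downside is that the table will include events due to COVID-19 itself, in both arms; the Suspected subset helps the reader there.

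Optional secondary point: if the Month 1 to 3 blood counts and metabolic panels are summarised, show them by arm with the number sampled and label them descriptive, because the draws are optional. With an assumed 300 subjects per arm (the allocation ratio is not stated), six abnormal values are 6/300 = 2.0% of the arm, but 6/150 = 4.0% of those tested at 50% uptake and 6/75 = 8.0% at 25%. This can be left to the SAP and adds no draws or visits.
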